8.3.2.3. Analysis Accounting for Visit Modality Change

There could be systematic differences between OHSA#1 scores collected during remote visits and OHSA#1 scores collected during in-clinic visits. Hence, a sensitivity analysis to assess the effect of visit modality on the primary efficacy analysis will be performed by adding a post baseline visit modality class variable with values “In-clinic” and “Remote” to the primary analysis model. The analysis will include all subjects in FAS. Week 4 LS mean and LS mean difference estimates and p-values will be provided.

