**Table 1: Schedule of Study Procedures**

Study Period:	Screening a (in clinic)	Treatment (All visits for each subject either in clinic or remote)					Follow-up
Study Day (Visit):	Day -28 to -7 (Visit 1)	Day 1 (Visit 2)	Day 8 (Visit 3) +/- 3 days	Day 15 (Visit 4) +/- 3 days	Day 22 (Visit 5) +/- 3 days	Day 29 (Visit 6) / ET +/- 3 days	Day 43o (Visit 7) +/- 3 days
Mandated Order of Procedures (when applicable)							
Informed consent	X						
Inclusion /exclusion criteria	X	X					
Medical history (including smoking history)	X b						
Concomitant medications (and smoking usage)	X b	X	X	X	X	X	X
MoCA	X						
OHQ subject training c	X c	X	X	X	X	X	
OHQ (OHSA and OHDAS)		X m	X	X	X	X	
PGI-C						X	
C-SSRS	X	X m,n	X n	X n	X n	X n	X
Tilt-table test	X d						
Randomization		X a					
Recommended Order of Procedures (when applicable)							
[REDACTED]		■				■	
[REDACTED]		■				■	

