### 8.3.1. Examination of Subgroups

Predefined subgroups will include, stratification stratum (i.e., disease type), gender, and smoking status. Additional subgroups may be predefined in the SAP.

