6.1.6. Examination of Subgroups

To assess consistency of treatment effect across subgroups, the primary analysis of OHSA#1 will be repeated for each of the following subgroups:

1. Disease Type: MSA, PD, and PAF
2. Gender: Male and Female
3. Timing of Primary Endpoint Visit Relative to COVID-19 Pandemic Onset:
Before 18MAR2020, On or After 18MAR2020

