8.3. Analysis of the Primary Efficacy Endpoint

8.3.1. Primary Efficacy Analysis

A mixed effects model for repeated measures (MMRM) incorporating the change from baseline in OHSA#1 as the dependent variable will be used to assess the primary endpoint hypothesis.

The model will include fixed class terms for treatment group and baseline disease type (MSA, PD, PAF), a covariate for baseline OHSA#1 score, and a time effect (week) and its interaction terms with treatment and baseline OHSA#1 score. An unstructured covariance structure (type=UN) to account for the repeated measures within a subject will be fitted. If the model doesn't converge, the data will be reanalyzed fitting a compound symmetric covariance structure (type=CS) and a compound symmetric with heterogenous variance covariance structure (type=CSH) and the structure with a lower AIC value will be selected.

Least squares (LS) mean change in OHSA#1 in each treatment group and the difference in LS mean change between treatment groups will be estimated. Point estimates, 95% confidence intervals (CIs), and p-values will be provided.

Figures

A plot will present the LS mean change from baseline in OHSA#1 at each postbaseline time point by treatment group with 95% CIs.

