8.3.2.4. Subgroup Analyses

To characterize the consistency of the treatment effect for the primary endpoint, the primary endpoint analysis will be repeated for the subgroups specified in Section 6.1.6.

The subgroup analyses will use the same analysis model and reporting structure as in Section 8.3.1. For the disease type subgroup analyses, the disease type stratum terms are redundant and will be omitted from the model. Subgroup analysis will not be performed when $n < 10$ or $n > N - 10$, where n is the number of FAS subjects in the subgroup and N is the number in the FAS.

For each subgroup, a plot of LS mean change from baseline in OHSA#1 at each postbaseline time point will be presented by treatment group with 95% CIs.

In addition, a forest plot of the difference between the treatment groups in LS mean change from baseline in OHSA#1 at Week 4 with 95% CI will be plotted. The x-axis will be difference in LS mean change from baseline and the y-axis will be the subgroups.

8.3.2.5. [REDACTED]

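### Is it a gap that SAP 8.3.2.3 adjusts OHSA#1 for visit modality without estimating the treatment effect separately for remote and clinic subjects?

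*SAP*

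**What the plan says.** SAP 8.3.2.3 gives its premise first: "There could be systematic differences between OHSA#1 scores collected during remote visits and OHSA#1 scores collected during in-clinic visits". The check that follows from it is worded thus: "to assess the effect of visit modality on the primary efficacy analysis will be performed by adding a post baseline visit modality class variable". That variable has two levels (in-clinic, remote) and joins the primary model; Week 4 LS means, their difference and p-values are reported for the FAS.

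The primary model in SAP 8.3.1 contains treatment, disease type, baseline OHSA#1 and "a time effect (week) and its interaction terms with treatment and baseline OHSA#1 score". No interaction with modality is named in either section.

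Consistency of effect is handled elsewhere. SAP 8.3.2.4 repeats the primary model by subgroup "To characterize the consistency of the treatment effect for the primary endpoint" and shows "a forest plot of the difference between the treatment groups in LS mean change from baseline in OHSA#1 at Week 4 with 95% CI". The subgroups, listed in SAP 6.1.6, are disease type, gender and "Timing of Primary Endpoint Visit Relative to COVID-19 Pandemic Onset", split at 18 March 2020. SAP section 10 adds a summary of visits by modality.

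The Protocol's Table 1 heads the treatment period "Treatment (All visits for each subject either in clinic or remote", and that period includes Visit 2, where baseline is taken and subjects are randomised. Under SAP 6.3.1 the first dose follows on the next morning.

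**The concern.** OHSA#1 is patient-reported, and for some subjects it is collected at home with a visiting nurse. The Protocol itself treats mixing of modalities as a source of variability. A statistician would naturally ask whether the drug effect is the same in both settings, and a main effect cannot answer that, because it forces one treatment difference on both.

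When modality is balanced between arms, adding the term barely moves the treatment estimate, whether the effect is uniform or confined to clinic subjects. Agreement between 8.3.2.3 and the primary analysis could then be read as evidence of a consistent effect, which it is not. The stake would be the interpretation of the result for remotely assessed subjects. The primary test, its error rate and the sample size are not involved.

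**Working it through.** **1. Trial size.** The subject numbers are redacted, but they can be recovered. Protocol 8.2 gives a difference of 1.5, SD 3.0, 90% power, two-sided 0.05 and 10% dropout; SAP 4.4 gives 1:1 allocation and an MSA floor of 40%, or 76 subjects.

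- Per arm: 2 × (1.960 + 1.282)² × 3.0² / 1.5² = 84.1, so 85 per arm and 170 in total.
- With dropout: 170 / 0.90 = 188.9, so 189, or 190 with equal arms.
- Check: 0.40 × 190 = 76, which matches the SAP.

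**2. What the additive model estimates.** Let p be the remote share, and dC and dR the treatment effects in clinic and remote subjects. With arms balanced within modality, the primary and the adjusted model both estimate (1 − p) × dC + p × dR. For dC = −1.5, dR = 0 and p = 0.25 this is 0.75 × (−1.5) = −1.13.

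A simulation of 2000 trials with the four-visit model of SAP 8.3.1 agrees. It assumed 172 subjects, change SD 3.0, within-subject correlation 0.6 and 25% remote.

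- Effect in clinic only: −1.13 primary and −1.13 adjusted, within 0.1 of each other in 94% of trials.
- Uniform effect with the same average: −1.13 and −1.13, within 0.1 in 99%.

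So agreement between the two analyses does not discriminate between these cases. The observation behind the concern is correct.

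**3. Whether the planned analysis does what it sets out to do.** Its premise is a difference in score level. In the same simulation, with an assumed 1-point remote shift, a uniform effect of −1.5 and unequal arms, the added term corrected the primary estimate by 0.05 (20% against 30% remote) and by 0.09 (15% against 35%). That is the task in 8.3.2.3. Because modality is fixed by Visit 2, before randomisation, such imbalance arises by chance, apart from later COVID-19 exceptions. The weighted average in step 2 is therefore a valid average treatment effect.

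**4. What a by-modality estimate would show.** Take 170 subjects and SD 3.0. The standard error in a stratum of n subjects is 3.0 × √(4/n), and the half-width is 1.96 times that. The chance that the remote interval includes zero when the true effect is −1.5 everywhere is about Φ(1.96 − 1.5/SE_remote). Interaction power uses √(SE_remote² + SE_clinic²) and a 1.5-point difference in effect. The remote share is assumed, since the documents give none.

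| Remote share | n remote / clinic | 95% half-width remote / clinic | Remote interval includes zero, true effect −1.5 | Interaction power |
|---|---|---|---|---|
| 10% | 17 / 153 | 2.85 / 0.95 | 82% | 16.5% |
| 20% | 34 / 136 | 2.02 / 1.01 | 69% | 25.6% |
| 30% | 51 / 119 | 1.65 / 1.08 | 57% | 32.1% |
| 50% | 85 / 85 | 1.28 / 1.28 | 37% | 37.1% |

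The simulated repeated-measures subgroup model at 25% remote gives a half-width of 1.85. Its SE is 1.85/1.96 = 0.944, and Φ(1.96 − 1.5/0.944) = Φ(0.37), about 64%. With the effect wholly absent in remote subjects, the average interval is 0.00 ± 1.85, which still contains −1.5.

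**5. The size rule.** SAP 8.3.2.4 skips a subgroup when n < 10 or n > N − 10. With two levels, fewer than 10 remote subjects puts the clinic group above N − 10, so both rows drop. At N = 170 this happens below 10/170 = 5.9% remote.

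**6. What cannot be read.** The SAP contents list shows section 8.3.2.5 on OHSA#1 completeness and visit modality, directly after the subgroup section and under the same heading of sensitivity and supplementary analyses. Its text is blacked out, as are SAP 12.1 and Protocol 8.7.1 on COVID-19 analysis strategies. Any of these may hold a by-modality estimate.

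**The case for a change.** The best case for the concern is that the remedy would cost almost nothing. Visit location is recorded in the database (Protocol Appendix 9), the subgroup model and forest plot exist, and Protocol 8.3.1 states "Additional subgroups may be predefined in the SAP". A wide interval would at least show how little is known about the remote effect, and the aim in 8.3.2.3 is phrased broadly enough to invite a reading about consistency. Pandemic timing is an imperfect substitute, because clinic visits remained available afterwards.

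Two parts of this stand. No visible output gives the effect by modality, and agreement between 8.3.2.3 and the primary analysis should not be cited as showing equal effects. Neither is a fault in the plan. The SAP does not make that reading; it assigns consistency to 8.3.2.4. That adjusting for a balanced factor hardly moves the estimate is true of any factor left out of 6.1.6, so it does not single out modality. The timing subgroup also gives some information: the remote option was introduced because of the pandemic, so the earlier group should be essentially clinic-only (an inference, as the approval dates are redacted).

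The extra row carries a misreading risk of its own. Under a uniform effect, the remote interval would often include zero, and modality is elected, so any contrast may reflect who chose remote visits.

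**Conclusion.** The concern does not hold. The modality analysis suits the question it states, the primary inference is unaffected, and no rule or figure in the plan is wrong. What is left is a preference for one more descriptive analysis of a self-selected factor. Its remote half-width would be about 1.3 to 2.9 points, against a design effect of 1.5, and it would change no planned conclusion.

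Those sizes rest on 170 evaluable subjects, SD 3.0, equal arms within modality and an assumed remote share of 10% to 50%; the simulated results also rest on assumed correlation, shift and effect patterns. The documents give no modality-specific effect and no reason to expect one. Because SAP 8.3.2.5, SAP 12.1 and Protocol 8.7.1 are redacted, it also cannot be said that the full plan lacks a by-modality analysis.

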8.3.2.4. Subgroup Analyses

To characterize the consistency of the treatment effect for the primary endpoint, the primary endpoint analysis will be repeated for the subgroups specified in Section 6.1.6.

The subgroup analyses will use the same analysis model and reporting structure as in Section 8.3.1. For the disease type subgroup analyses, the disease type stratum terms are redundant and will be omitted from the model. Subgroup analysis will not be performed when $n < 10$ or $n > N - 10$, where n is the number of FAS subjects in the subgroup and N is the number in the FAS.

For each subgroup, a plot of LS mean change from baseline in OHSA#1 at each postbaseline time point will be presented by treatment group with 95% CIs.

In addition, a forest plot of the difference between the treatment groups in LS mean change from baseline in OHSA#1 at Week 4 with 95% CI will be plotted. The x-axis will be difference in LS mean change from baseline and the y-axis will be the subgroups.

8.3.2.5. [REDACTED]

8.4. Analysis of Secondary Efficacy Endpoints

8.4.1. Analysis of Change From Baseline in OHSA and OHDAS Composite Score

The following two secondary efficacy endpoints will be analyzed in the same way as the primary efficacy endpoint, as described in Section 8.3.1, using the baseline value of the endpoint as the covariate:

- Change from baseline in OHSA composite score in Weeks 1 to 4
- Change from baseline in OHDAS composite score in Weeks 1 to 4

The hypothesis testing schema is similar to the primary efficacy endpoint for the treatment comparison, i.e., no difference between ampreloxetine (TD-9855) (active) group and the placebo.

Figures

Plots will present the LS mean change from baseline at each postbaseline time point by treatment group with 95% CIs for OHSA and OHDAS composite scores.

8.4.2. Analysis of PGI-C and Incidence of Falls

There are two binary secondary efficacy endpoints and their analyses are described below.

Patient Global Impression of Change (PGI-C)

PGI-C is a 5-point scale depicting the overall change in a patient’s neurogenic orthostatic hypotension symptoms since the initiation of study medication. Patients rate their change as “Much better,” “A little better,” “No change,” “A little worse,” or “Much worse.” Early versions of the protocol (original and Amendment 1) used the PGI-C on a 7-point scale. For analysis purposes, the 7-point scale will be mapped to the 5-point scale (Table 4). However, the data will be listed as collected.

The PGI-C will be summarized as number and percentage of subjects with “better” and “no change or worse” at Week 4 (see Appendix 1).

The proportion of subjects with PGI-C responses indicating improvement and the proportion with at least one fall will be compared between treatment groups using a Cochran-Mantel-Haenszel chi-squared test stratified by disease type at baseline.

Table 4: Mapping of PGI-C From 7-Point Scale to 5-Point Scale

7-Point Scale	5-Point Scale
Very Much Improved	Much Better
Much Improved	
Minimally Improved	A Little Better
No Change	No Change
Minimally Worse	A Little Worse
Much Worse	Much Worse
Very Much Worse	

In case the treatment groups differ substantially with respect to timing of assessment, the PGI-C analysis will be supplemented by a sensitivity analysis restricted to subjects with PGI-C collected within the narrowed window study day 25 to 42.

A plot will be presented to show the CMH-weighted average proportion of subjects with PGI-C responses indicating improvement by treatment group at Week 4.

Incidence of falls

Incidence of falls will be summarized as number and percentage of subjects with at least one fall during the interval from the date of the first dose to the date of the last dose.

The falls analysis will be supplemented by corresponding analyses of the incidence of at least one near-fall and of the incidence of at least one fall or near-fall, and by generalized linear model-based analyses of the reported number of falls, near-falls, and falls or near-falls during the treatment period. For these count analyses, the null and alternative hypotheses will be

$$H_0: \theta = 1$$

$$H_1: \theta \neq 1$$

where θ is the TD-9855:placebo weekly incidence density ratio of falls (or near-falls, or either) during the evaluation period. The analyses will be performed by fitting a generalized linear model with a negative binomial error distribution, log link, and log time at risk in weeks as the offset, including disease type stratum and the pre-treatment weekly incidence rate of falls (or near-falls, or either) as covariates. For purposes of this analysis, the pretreatment period will be defined as beginning on the date of the screening visit and ending on the day before the first dose date.

Analysis results provided will include the model-based estimates of weekly incidence rate for each treatment group and point and interval estimates of their ratio, and descriptive statistics for the number of events per patient week during the pretreatment period and during the evaluation period. For falls, this will be calculated as:

$$7 \times (\text{total number of falls reported}) / (\text{evaluation end date} - \text{first dose date} + 1)$$

The incidence rate will be calculated likewise for near-falls and for falls and near-falls combined.

A plot will be presented to show the CMH-weighted average proportion of subjects with at least one fall during the treatment period by treatment group.

8.4.3. Multiplicity Adjustment

If a statistically significant treatment effect has been demonstrated for the primary efficacy endpoint, the following secondary efficacy endpoints will be tested in a hierarchical fashion in the order below using 2-sided tests at the 5% level of significance until a failure to reject the null hypothesis occurs:

- Change from baseline in OHSA composite score at Week 4
- Change from baseline in OHDAS composite score at Week 4
- PGI-C at Week 4
- Incidence of falls during treatment

For all other analyses, including additional analyses of the primary efficacy endpoint, analyses of the other secondary efficacy endpoints change from baseline in OHSA composite score in Weeks 1 to 3 and change from baseline in OHDAS composite score in Weeks 1 to 3, and analyses of exploratory endpoints, unadjusted p-values and nominal 95% CI intervals will be provided.

8.5. Analysis of Exploratory Efficacy Endpoints

[REDACTED]

[REDACTED]

[REDACTED]

[REDACTED]

[REDACTED]

[REDACTED]

[REDACTED]

[REDACTED]

[REDACTED]

[REDACTED]

█ [REDACTED]

8.5.2. [REDACTED]

[REDACTED]

[REDACTED]

- █ [REDACTED]
- █ [REDACTED]
- █ [REDACTED]
- █ [REDACTED]
- █ [REDACTED]
- █ [REDACTED]
- █ [REDACTED]

8.6. Scoring and Analysis of Clinical Outcome Assessments

This section discusses the scoring of clinical outcome assessments and provides additional details on their analyses.

8.6.1. OHQ

The Orthostatic Hypotension Questionnaire (OHQ) includes two parts, the Orthostatic Hypotension Symptom Assessment (OHSA) to measure the presence and severity of symptoms and the Orthostatic Hypotension Daily Activity Scale (OHDAS) to measure the impact of orthostatic symptoms on daily activities. Recall period is “over the past week.”

OHSA consists of six questions, each rating the intensity of one characteristic symptom of NOH:

1. Dizziness, lightheadedness, feeling faint, or feeling like you might black out
2. Problems with vision (blurring, seeing spots, tunnel vision, etc.)
3. Generalized weakness
4. Fatigue
5. Trouble concentrating
6. Head/neck discomfort

OHDAS consists of four questions that assess the impact of NOH symptoms on daily activities.

The items are scored on an 11-point scale from 0 to 10, with 0 indicating no symptoms/no interference and 10 indicating the worst possible symptoms/complete interference. OHDAS has an option of selecting “cannot be done for other reasons,” which will not be included in scoring.

OHSA and OHDAS composite scores are an unweighted average of the scores of their nonmissing constituent items. The OHQ overall composite score will be calculated as

$$\frac{(\text{Sum of nonmissing OHSA item scores} / \text{Number of nonmissing OHSA items} + \text{Sum of nonmissing OHDAS item scores} / \text{Number of nonmissing OHDAS items})}{2}$$

The calculated OHSA and OHDAS composite scores and the OHQ overall composite score will be rounded to the nearest 0.1.

OHSA#1 is assessed as the primary efficacy endpoint and its analysis is described in Section 8.4.1. Additionally, composite scores of OHSA and OHDAS, OHQ overall composite score, and individual item scores for OHSA items 2-6 and OHDAS items 1-4 will be analyzed similarly.

8.6.2.

[REDACTED]

[REDACTED]

[REDACTED]

[REDACTED]

[REDACTED]

[REDACTED]

m [REDACTED] es [REDACTED] ue [REDACTED]
er ue [REDACTED] num [REDACTED] ue [REDACTED]

[REDACTED]

[REDACTED]

[REDACTED]

[REDACTED]

[REDACTED]

8.6.5. [REDACTED]

[REDACTED]

[REDACTED]

[REDACTED]

[REDACTED]

8.6.8. [REDACTED]

[REDACTED]

[REDACTED]

[REDACTED]

[REDACTED]

[REDACTED]

[REDACTED]

[REDACTED]

[REDACTED]

[REDACTED]

[REDACTED]

9. Safety and Tolerability

The analysis of safety and tolerability data includes an overall summary of adverse events, drug exposure (duration of treatment), dosing information/compliance, concomitant medications, clinical laboratory results, vital signs, ECGs, and C-SSRS.

In general, inferential statistical tests are not performed for the analyses of safety and tolerability data.

For all safety analyses, the safety analysis set will be used. The listing of TEAE and vitals signs will be provided using the randomized analysis set to include the subjects from site 27045.

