**Orthostatic Hypotension Daily Activities Scale (OHDAS)**

We are interested in how the low blood pressure symptoms you experience affect your daily life. Please rate each item by circling the number that best represents how much the activity has been interfered with *on the average* over the past week by the low blood pressure symptoms you experienced.

If you cannot do the activity for reasons other than low blood pressure, please check the box at the right.

1. Activities that require standing for a short time

No Interference 0 1 2 3 4 5 6 7 8 9 10 Complete Interference  CANNOT DO FOR OTHER REASONS

2. Activities that require standing for a long time

No Interference 0 1 2 3 4 5 6 7 8 9 10 Complete Interference  CANNOT DO FOR OTHER REASONS

3. Activities that require walking for a short time

No Interference 0 1 2 3 4 5 6 7 8 9 10 Complete Interference  CANNOT DO FOR OTHER REASONS

4. Activities that require walking for a long time

No Interference 0 1 2 3 4 5 6 7 8 9 10 Complete Interference  CANNOT DO FOR OTHER REASONS

THR173023\_0169\_OHQ\_English(US)\_v1.0\_2018\_Aug\_01.doc

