6.3.2. Change from Baseline

Change from baseline is calculated as postbaseline result – baseline result.

If either the baseline or the postbaseline result is missing, the change from baseline is set to missing.

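### Can items moved to or from the OHDAS 'cannot do' box distort the composite enough to need a same-item analysis?

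*SAP*

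**What the plan says.** Protocol Appendix 2-1 prints a box beside each of the four OHDAS items: "If you cannot do the activity for reasons other than low blood pressure, please check the box at the right". SAP 8.6.1 treats that response as one "which will not be included in scoring" and then averages what remains: "OHSA and OHDAS composite scores are an unweighted average of the scores of their nonmissing constituent items". The visible text sets no minimum number of scored items and does not require the same items at baseline and follow-up.

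SAP 6.3.2 works on whole results: "If either the baseline or the postbaseline result is missing, the change from baseline is set to missing". SAP 8.4.1 analyses the composite with the primary MMRM, "using the baseline value of the endpoint as the covariate". In SAP 8.4.3 the secondaries are "tested in a hierarchical fashion in the order below", and the second of the four is "Change from baseline in OHDAS composite score at Week 4".

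Three other provisions matter. SAP 8.6.1 adds that "individual item scores for OHSA items 2-6 and OHDAS items 1-4 will be analyzed similarly". Protocol 8.1 has all subject data listed as they were collected. Footnote c to Protocol Table 1 has subjects retrained before every OHQ. OHSA has no such box and is unaffected.

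Protocol 8.7, SAP 8.5, most of SAP 8.6.2 onward and SAP 12 are blacked out, so the absence of an item-matching rule is shown for the visible text only.

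**The concern.** A change score should compare the same thing at two times. Here a subject can appear to improve because the two hardest activities left the average, or to worsen because they came back. The sign can even reverse: with assumed scores, 4, 8, 4, 8 (mean 6.0) becoming 5, box, 5, box (mean 5.0) records a change of -1.0, although both items still scored got worse by 1.

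OHDAS at Week 4 is a confirmatory secondary, and PGI-C and falls are tested only if it succeeds. If one arm ticked or unticked the box more often, part of the estimated effect would reflect a changed item set. The visible sensitivity and supplementary analyses in SAP 8.3.2 all concern OHSA#1, so none recomputes the OHDAS composite on a fixed set of items.

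**Working it through.** The documents give no figure for this rule, so the check is the algebra of the score followed by its effect on the test.

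**Shift for one subject.** If k of the 4 items leave and the rest stay the same,

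shift = -(k/4) × (mean of items that left - mean of items kept).

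Assumed baseline 4, 7, 4, 7 (short items 4, long items 7; mean 5.5):

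- one long item boxed: -(1/4) × (7 - 5) = -0.5, composite 5.0
- both long items boxed: -(2/4) × (7 - 4) = -1.5, composite 4.0
- one short item boxed: -(1/4) × (4 - 6) = +0.5, composite 6.0
- all items equal, or the same box ticked at both visits: 0

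**Bias between arms** = (difference in switching rates) × (shift). Equal rates give zero.

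**Precision.** The sample size is redacted. Protocol 8.2 gives a difference of 1.5, SD 3.0, 90% power and two-sided 0.05, which needs 86 per arm by the t-based calculation (power 90.3%). SAP 4.4 agrees: 76/0.40 = 190 randomised, and 190 × 0.9 = 171 after 10% dropout. The SD of OHDAS change is not given. Assuming 2.1, SE = 2.1 × √(2/86) = 0.320.

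**Type I error** when the true OHDAS effect is zero = Φ(-1.96 + b/SE) + Φ(-1.96 - b/SE), where b is the size of the bias:

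| Items boxed | Arm difference (points) | b | Closed form | Simulated |
|---|---|---|---|---|
| one long | 5 | 0.025 | 5.1% | 5.2% |
| one long | 10 | 0.050 | 5.3% | 5.3% |
| one long | 20 | 0.100 | 6.1% | not run |
| both long | 5 | 0.075 | 5.6% | 5.4% |
| both long | 10 | 0.150 | 7.6% | 6.9% |
| both long | 20 | 0.300 | 15.5% | 12.7% |

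The simulation used the SAP 8.3.1 model at four visits (correlation 0.7, unstructured covariance, complete data), with items rounded and limited to 0-10. Boxes were newly ticked at every post-baseline visit in one arm and never in the other. There were 6000 replicates per case, a simulation error of about 0.3 percentage points. With no boxes the rate was 5.0%.

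**Range over the assumed SD** (1.3 / 2.1 / 2.6), simulated: one long item at 10 points, 5.6 / 5.3 / 4.9%; both long at 10 points, 10.8 / 6.9 / 6.1%; both long at 20 points, 29.8 / 12.7 / 9.1%.

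**Balanced switching** (10% in each arm, both long items): SE 0.326 against 0.321 on a same-item score at SD 2.1, and 0.204 against 0.195 at SD 1.3. This is a small loss of precision and no bias.

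**What the planned item analyses show.** Under SAP 6.3.2 an item boxed at either visit has no change score, so each item analysis compares like with like. With both long items boxed at 10% against 0%, the simulated item effects averaged about 0.01, while the composite was off by 0.12 to 0.14 in separate runs. Setting the four item estimates beside the composite would expose the drift.

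**Other ways to score a box.** For 4, box, 4, box, scoring the box as 10 gives (4 + 10 + 4 + 10)/4 = 7.0, a shift of +1.5. Scoring it as 0 gives (4 + 0 + 4 + 0)/4 = 2.0, a shift of -3.5. Leaving the item out shifts the score by -1.5. No simple substitute is clearly better.

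**The case for a change.** The best case for acting is that this is a gated confirmatory endpoint and that a check would cost one model and one table on data already held. It would also carry more weight if written down before unblinding. Box status could change for real reasons: Protocol 6.4.6.7 says that falls can injure and that fear of falling limits mobility. If placebo subjects fell more and boxed the long items, placebo would look better and a true benefit could be hidden. Retraining and blinding do not prevent a genuine change in what a person can do. Each item analysis also rests on a different subset of subjects and is not a check of the composite itself.

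Much of this stands as description: no visible analysis pools the items on a matched basis. It does not show a gain from changing the plan. The route through falls is an inference with no rate behind it, and the box is reserved for reasons unrelated to low blood pressure, the symptom the drug targets. The prespecification argument is largely met because the item analyses are already in the SAP.

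A same-item score has costs too. It selects items by a response given after randomisation, gives subjects different item sets, and still carried a residual bias of up to 0.045 in the simulations. It also disagreed with the planned score on significance in 3.0, 5.8 and 13.4% of null trials at 5, 10 and 20 points (both long items, SD 2.1). A rule that such disagreement should cast doubt on later tests would reach PGI-C and falls, which do not use OHDAS scoring.

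**Conclusion.** No change is needed. The scoring rule is disclosed and is a fair way to handle an activity a subject cannot do for unrelated reasons. It can move an individual change score with no scored item changing. It biases the comparison only if switching differs by arm, which nothing in the documents suggests.

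At an assumed SD of 2.1 and a 3-point gap between long and short items, differences of 5 points, or of 10 points with one long item, leave type I error at 5.2% to 5.4%. Larger inflation needs both long items newly boxed in one arm only, at 10% to 20%, and is worst if the SD is as low as 1.3. Even then the rates apply only if OHSA#1 and the OHSA composite have both been rejected and the true OHDAS effect is zero.

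The planned item 1 to 4 analyses would reveal most of any drift, and the listings will hold the box responses, so an analyst can count them by item, arm and visit when reporting without amending the plan. The switching rates, item gap and OHDAS SD are all assumptions, and redacted sections may already contain a rule.
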